9.2.4 Investigator Selection Criteria

University centers and outpatient clinics qualified by training and experience in the management of patients with CHC will be selected to participate in this study. The AbbVie Affiliate Medical Director will ensure that sites participating in the study are representative of the medical practice in the country, have the ability to conduct the study and their availability of the target patient population. The type of the participating treating institute will be documented in the eCRF.

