9.7.3.3 Statistical Methods for Analysis of Effectiveness Variables

The simple percentage of patients achieving SVR12 will be calculated and an exact two-sided 95% confidence interval (CI) of the percentage will be computed based on the Clopper-Pearson method.

Corresponding methods will be used for other response rates (EoT response rate, relapse rate, viral breakthrough). The relapse rates will be estimated in patients of the CP analysis groups with EoT response and sufficient HCV RNA measurements post-treatment. Viral breakthrough rates will be estimated in all patients of the CP analysis groups, who have at least one undetectable HCV RNA measurement on-treatment and at least one on-treatment or EoT measurement thereafter.

Univariate and multiple logistic regression (MLR) methods will be used to investigate the impact of the following explanatory covariates on SVR12:

- Key demographic information
- Mode of CHC infection
- HCV RNA level at baseline
- Most recent stage of liver fibrosis
- HCV genotype and subtype (if available)
- Type of treating institute
- Liver and/or CHC related co-morbidities
- Key clinical chemistry and hematology laboratory variables at baseline
- In treatment experienced patients only:
 - Most recent prior treatment for CHC
 - Outcome of most recent prior CHC treatment

Further details and additional covariates will be specified in the SAP.

These analyses will be of exploratory nature, data driven, and will be repeatedly performed for various CP Analysis Groups, since not each covariate might be

predictive in each patient group. Furthermore, the fact that treatment regimens will differ in the various patient groups has to be taken into account, when selecting the patient groups for each MLR analysis. Backward selection procedures will be applied to generate the final MLR models which consider only covariates in the selection procedure with a p-value <0.25 in the corresponding univariate logistic regression analysis. A p-value <0.05 will be used for the covariates to stay in the model in a backward elimination step. Logistic regression methods will also be used to investigate the impact of treatment adherence on SVR12.

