9.9 Limitations of the Research Methods

The limitations of observational studies, such as uncontrolled confounding by lack of randomization, and difficulties to clearly interpret treatment effects in the context of missing data are well known. Their validity can be increased by accurate outcome measurements, documentation of the most common confounders, sufficient length of follow-up and by activities to obtain complete recording of available data as well as by searches for missing key data.

The most important outcome measure in this study is HCV RNA. Missing or unrecorded follow-up HCV RNA data can in particular lead to an underestimation of the real SVR rate as compared to the SVR rate of interventional trials. Highly sensitive and quantitative diagnostic tests are required to measure HCV RNA levels in blood. In an observational study each center will be using its own test – either commercially available or so-called “home-brew” tests – which might change from one visit to the next within a patient data set. The challenge is to accurately and consistently document test properties such as the LLoD and the LLoQ to put the results into perspective of prior outcomes from randomized controlled trials with (usually) central laboratory assessments for all trial participants.

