# 3. STUDY DESIGN

# 3.1 Overview of Study Design and Dosing Regimen

This is a prospective, multi-center observational study in adult patients chronically infected with HCV receiving the interferon-free ABBVIE REGIMEN ± RBV.

University centers and outpatient clinics qualified by training and experience in the management of patients with CHC participate in this study.

The prescription of a treatment regimen is at the discretion of the physician in accordance with local clinical practice and label, is made independently from this observational study and precedes the decision to offer the patient the opportunity to participate in this study.

After written patient authorization has been obtained, patient data including demographic data, HCV disease characteristics, co-morbidities, co-medication, treatment details, and laboratory assessments as recorded in the patient's medical records (source documentation) are documented in the electronic case report form (eCRF). Patients are observed for the duration of the ABBVIE REGIMEN therapy and for up to 24 weeks after treatment completion.

[figure not shown]
The observational period for patients receiving 12 weeks of ABBVIE REGIMEN is max. 36 weeks (12 weeks treatment and 24 weeks post-treatment observation) and for patients receiving 24 weeks of ABBVIE REGIMEN the observational period is max. 48 weeks (24 weeks treatment and 24 weeks post-treatment observation).

Follow-up visits, treatment, procedures and diagnostic methods follow physicians' routine clinical practice. The observational study period entails the following data collection schemes, data documented are those closest to the time windows as indicated in Figure 1:

- 12-week treatment regimen: four visits plus two interim data collection windows
- 24-week treatment regimen: four visits plus three interim data collection windows

This schedule is based on the anticipated regular follow-up for patients undergoing treatment for CHC.

Figure 1 - Study Flowchart

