**Table 2 - Data Documentation Schedule** 

Assessment/ Procedure		Treatment Period		Post-treatment (PT) Period			
(only available data to be collected; no diagnostic or monitoring procedures to be applied to the patients apart from those of routine clinical practice)	Baselin	On- treatment visits	Mid treatment visit for pts receiving 24 weeks of therapy	EoT b	Early PT visit	SVR 12 visit	SVR 24 visit
Patient authorization	X a						
Demographic information	Χ						
IL28B	Χ						
Relevant CHC disease characteristics	Х						
Liver fibrosis stage	Х						
CHC treatment history	Χ						
HCV genotype and subtype	Χ						
HCV RNA samples	Х	Х	Х	Х	Х	Χ	Χ
Clinical chemistry and hematology	Χ	Х	Χ	Х	Х	Х	Х
ABBVIE REGIMEN initiation documentation	Х						
ABBVIE REGIMEN adherence		Х	Χ	Х			
Concomitant medication	Χ	Х	Χ	Χ			
Relevant medical history, co-morbidities	Χ						
sAE, AE and pregnancy reporting	Х	Х	Х	Х	Xc	$X_q$	Xd
For patients receiving RBV: Evidence, in accordance with local label, that female patient or female partner of male patient is not pregnant	Х						
Patient questionnaires – WPAI, EQ5D-5L	Χ			Х		X	Х

Abbreviations: EoT = End of Treatment (at Week 12 or 24 or at premature discontinuation), PT = Post-Treatment

- a Written patient authorization must be obtained before any data documentation in the eCRF
- b Patients who prematurely discontinue should return to the site to document EoT data
- c Tolerability documentation until PT week 4
- d Pregnancy reporting for patients treated with DAA plus RBV

In accordance with the non-interventional nature of the study all HCV RNA measurements will be performed at the sole discretion of the physician and all HCV RNA measurements have to be entered into the eCRF. All recorded HCV RNA values will be assigned to appropriate time points (baseline, on-treatment visits, EoT visit, post-treatment visits) as follows:

Table 3 - Analysis Time Windows for HCV RNA

Phase	Time point	Time Window
Pre-Treatment	Baseline	Last value prior to start of study treatment (i.e.
		≤study day 1)
On-treatment		Study day during treatment period^#
		(Study day 1 = first treatment day)
Treatment Week	4 (RVR*)	15 - 42^
EoT	Actual EoT	Study day of last dose#
		(28 days prior to last dose - 7 days post last
		dose)
Post Treatment	12 weeks (SVR 12	>=70-126 days post last dose
	window)	
	24 weeks (SVR24	127-210 days post last dose
	window)	

^values must also be <= 7 days post last dose

#>=study day 2

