#### 4.2.4 Site and Researcher Information

Data of the study sites and of the Researcher will be presented in summary tables and listings.

The summary tables for site information will show absolute and relative frequencies for the institution type (private practice/ private hospital, general hospital, academic/ university hospital, other), the type of unit (general population, transplant, drug user, HIV/ HCV co-infection, hepatocellular carcinoma [HCC]), and the site location (urban, rural). Regarding type of unit multiple answers per site are possible.

The principle researcher experience will be summarized by presenting for each therapeutic specialty (hepatology, infectious disease, gastroenterology, internal medicine, transplant, general practitioner) the number and percentage of principle researchers, who have the specific experience. Furthermore, the number and percentage of sites with at least one researcher (i.e. including co-researcher) of the therapeutic specialty concerned and the number of HCV-infected patients typically seen per month at the site (<25, 25-50, 51-75, 76-100, >100), including the patients seen by co-researcher, will be summarized. Note: Multiple therapeutic specialties could be reported per researcher.

An overview of Tables for site and researcher information is given in Table 5.

Table 5 Overview of Outputs for Site and Researcher Information

Output Title	Output Short Name	Analysis Population
Site Information - <country></country>	tsi_ <c></c>	Sites with patients
Researcher Experience- <country></country>	tre_ <c></c>	Sites with patients

The layouts of the tables mentioned above are provided in Part II of the SAP (Table Shells).

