#### **SVR24 (Exploratory Analyses)**

Univariate and multiple logistic regression (MLR) methods will be used to investigate the impact of various explanatory covariates (patient and disease characteristics) at baseline on SVR24.

These analyses will be of exploratory nature, data driven, and will be performed for CP population. Univariate logistic regression will be performed first and then backward selection procedures will be applied to generate the final MLR model. A p-value <0.05 will be used for the covariates to stay in the model in a backward elimination step. If the percentage of patients with available data for a variable is lower than 80% of the patient group analyzed, then this variable will not be considered in the MLR analysis.

The variables to be considered are as follows:

- · Key demographic information
  - o Age (continuous)
  - o Gender (Female [reference], Male)
  - Race/ethnic origin (White/Caucasian [reference], Black, Asian/Oriental, Other [all other races]); at least two categories with at least 10% of the patients each have to exists, so that this variable will be considered
  - Weight (continuous)
  - o BMI (continuous)
  - IL28B, rs12979860 (CC [reference], CT or TT); patients with unknown genotype are excluded from the respective analyses.
- CHC disease characteristics
  - Years since diagnosis (continuous)
  - Mode of CHC infection (Drug use [reference], Other [all other answers excluding unknown], unknown);
  - Most recent stage of liver fibrosis (No cirrhosis/Transition to cirrhosis [reference],
     Cirrhosis; for definition see 4.2.6.2);
- HCV RNA level at baseline (log10 IU/mL)
- HCV genotype( G1a\*, G1b, G4; for definition see section 4.2.6.2)
- Type of treating institute (Private Practice / Private Hospital, Academic / University Hospital, General Hospital, Other)
- Co-infections (every patient not reporting the respective co-infection is considered as not having the respective co-infection)
  - o HIV(No [reference], Yes)
  - HBV(No [reference], Yes)
- Liver and/or CHC related co-morbidities (every patient not reporting the respective co-morbidity is considered as not having the respective co-morbidity)
  - o Liver transplantation (No [reference], Yes)
  - Steatosis (non-alcoholic) (No [reference], Yes)
  - o Decompensated liver disease (No [reference], Yes)
- Other co-morbidities (every patient not reporting the respective co-morbidity is considered as not having the respective co-morbidity)

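### Type of treating institute is a site attribute, but it is tested in patient-level logistic regression with no allowance for site, so variation between sites can be reported as an institute-type effect

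*SAP*

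**What the plan says.** The SAP's exploratory SVR24 section (within 4.2.7.2.1) states: "Univariate and multiple logistic regression (MLR) methods will be used to investigate the impact of various explanatory covariates". The analysis is in the core population. Univariate models come first, then backward elimination with p below 0.05 needed to stay. One listed covariate is "Type of treating institute (Private Practice / Private Hospital, Academic / University Hospital, General Hospital, Other". The adherence regressions in the same SAP section reuse these covariates and methods. Protocol 9.7.3.3 lists the same covariate for SVR12: "Univariate and multiple logistic regression (MLR) methods will be used to investigate the impact of the following explanatory covariates on SVR12".

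Both documents treat institute type as a property of the site. Protocol 9.2.4 says: "The type of the participating treating institute will be documented in the eCRF". SAP 4.2.4 says: "The summary tables for site information will show absolute and relative frequencies for the institution type". The design is clustered: "This is a prospective, multi-center observational study in adult patients chronically infected with HCV" (SAP 3.1).

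Neither document names a site term, a random effect, GEE, a cluster-robust variance or any other allowance for patients sharing a site. Neither gives the number of sites or an ICC.

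Three provisions bear on how far sites may differ:
- On testing, SAP 4.2.2 says "all HCV RNA measurements will be performed at the sole discretion of the physician".
- SAP 4.2.3 counts a value still missing after imputation as a failure.
- On assays, Protocol 9.9 says "In an observational study each center will be using its own test".

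**The concern.** For a covariate that is constant within a site, the information comes from the number of sites of each type. An ordinary logistic regression counts every patient as a separate observation. Its reference distribution for institute type is right only if sites of the same type share one response probability. Otherwise the standard error is too small.

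Week-24 retesting is the clearest route to such differences. The SAP reports the SVR24 rate itself in the core population with sufficient follow-up, which drops responders lost for reasons unrelated to safety or effectiveness. The regressions use the full core population, where those patients count as failures. A site that seldom retests at week 24 therefore has a lower SVR24 rate in the regression, whatever its patients' virological outcome.

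At stake is secondary objective 2, predictive factors of response. Institute type is the only provider-level factor in the covariate list. The SAP introduction names provider- and system-level factors as a reason why effectiveness research is relevant to policy-makers. A few sites with poor retesting could make one type of hospital look predictive.

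**Working it through.** **Inputs from the documents.** 360–380 evaluable patients; planning SVR12 rates of 90% and 95% (SAP 3.2); retention at p < 0.05; four institute categories, so up to 3 df.

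**Assumptions.** The SVR24 rate equals the SVR12 planning rate. There are 10, 20 or 40 sites. The ICC is 0 to 0.10.

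**Step 1: the plan's own figure.** The only precision figure in the plan is the Clopper-Pearson width for SVR12. For 324/360 the limits are 86.43 and 92.90, width 6.47; the SAP prints 6.5. The other five rows also reproduce to rounding. No figure is given for the regressions.

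**Step 2: design effect.** With N = 370 (mid-range), S sites and m = 370/S patients per site, DE = 1 + (m − 1) × ICC. The true error of a nominal 5% test is:
- 1 df: 2[1 − Φ(1.96/√DE)]
- 3 df: P(χ²₃ > 7.815/DE)

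For 20 sites m = 18.5. At ICC 0.05, DE = 1 + 17.5 × 0.05 = 1.88.

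| Sites | ICC | DE | 1 df | 3 df |
|---|---|---|---|---|
| 20 | 0.01 | 1.18 | 7% | 8% |
| 20 | 0.02 | 1.35 | 9% | 12% |
| 20 | 0.05 | 1.88 | 15% | 24% |
| 20 | 0.10 | 2.75 | 24% | 42% |
| 10 | 0.02 | 1.72 | 13% | 21% |
| 10 | 0.05 | 2.80 | 24% | 43% |
| 40 | 0.01 | 1.08 | 6% | 7% |
| 40 | 0.05 | 1.41 | 10% | 14% |

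**Step 3: simulation.** Site rates were drawn from a beta-binomial model with no institute effect: 380 patients, 90% response, sites of unequal size, type assigned by site. The likelihood-ratio test at nominal 5% rejected as follows with 20 sites:

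| ICC | 2 types | 3 types |
|---|---|---|
| 0.02 | 12% | 14% |
| 0.05 | 20% | 27% |
| 0.10 | 29% | 44% |

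- At ICC 0 the rate is about 5%.
- At ICC 0.01 with 20–40 sites it is 6–9%.
- Over ICC 0.02–0.10 it runs from 15% to 57% with 10 sites, and from 9% to 27% with 40.
- With all four categories it is higher. For 370 patients, 20 sites and 90% response at ICC 0.01, it is 9% with equal and 11% with unequal site sizes.

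**Step 4: what these ICCs mean.** The between-site SD is √(ICC × p(1 − p)). At p = 0.90 this is √(0.02 × 0.09) = 4.2 points for ICC 0.02 and √(0.05 × 0.09) = 6.7 points for ICC 0.05. In the beta model, ICC 0.05 puts the central 95% of site rates between 73.5% and 98.8%, which is a wide spread.

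Retesting alone could produce values in this range. Suppose biological response is 95% everywhere and a fraction r of a site's patients is retested, so the site rate is 0.95r.
- Mean r 95%, SD 5 points: ICC = (0.95 × 0.05)² / (0.9025 × 0.0975) ≈ 0.026.
- Mean r 90%, SD 10 points: ICC = (0.95 × 0.10)² / (0.855 × 0.145) ≈ 0.073.

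These retest rates are illustrative, not taken from the documents.

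**Step 5: the site as the unit.** In the Step 3 simulations, an F-test that divides the likelihood ratio by max(1, Pearson dispersion) rejects in about 1–11% of runs, above nominal at high ICC. In a separate set with 370 patients, a weighted F-test on site rates rejects in 3.1–5.6%.

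**The case against.** **The analysis is exploratory, and this is one covariate of 27.** If all 27 were null and tested independently at 5%, 27 × 0.05 = 1.35 false signals would be expected. Raising one of them to 12–20% adds only 0.07–0.15. Backward selection and data-driven merging of categories already weaken any nominal p-value. This limits the importance of the point. It does not answer it, because an exploratory label excuses multiplicity but does not correct a standard error built on the wrong unit.

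**The size is unknown.** This stands. With 40 sites and ICC 0.01 the inflation is negligible, and the largest figures come from few sites or an ICC that implies very different sites.

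**Assay differences are partly handled.** This also stands. SAP 4.2.3 counts a result as response only if a PCR test was used with a detection or quantification limit of at most 50 IU/mL. Local assays are therefore held to one threshold, and sensitivity matters mainly where a limit exceeds 50. Retesting is the stronger mechanism.

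**Independence is inferred.** The SAP does not state it. It follows from the plain method named and the absence of any clustering method; the table shells in SAP Part II are not available.

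A reader might infer that the test will declare an institute effect whenever sites differ. The documents do not support that: they do not establish how far sites differ, and in most simulated cells with real site variation the test still usually does not reject.

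**Conclusion.** The point holds in conditional form. Institute type is constant within a site, and the named model makes no allowance for site. If sites of the same type differ in response or retesting, that difference can be reported as an institute effect, and the p-value and interval for this covariate are too optimistic.

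Under the stated assumptions (380 patients, 90% response, two or three types), false rejection at nominal 5% is about 6–9% at ICC 0.01 with 20–40 sites. It is 12–27% at ICC 0.02–0.05 with 20 sites, and higher with 10 sites or ICC 0.10. All of this rests on a number of sites and an ICC that the documents do not give.

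It would be tempting to extend the point to the study's main result. The primary SVR12 estimate does not use these models and is unaffected. The consequence is confined to one covariate in an exploratory secondary analysis and to the adherence models that reuse it.

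**What to change.** In SAP 4.2.7.2.1, for the SVR24 and adherence models, state that:

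- Institute type is judged for retention, and reported, with the site as the unit. Use either an overdispersion-scaled site-level F-test or a permutation of institute type across sites. The F-test can exceed 5% at high ICC, and a simple permutation does not adjust for the other covariates; the SAP should say so.
- The number of sites in each institute category is shown beside the estimate.
- If a category has too few sites, institute type is reported descriptively and left out of backward selection.

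A random site intercept in all models is optional. At 90–95% response, 380 patients give only 380 × 0.05 = 19 to 380 × 0.10 = 38 failures, about one or two per site with 20 sites. Such a model may be unstable alongside a long covariate list, and it was not simulated here.

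The cost is a few sentences and modest programming, with no new data. SAP 6.1 already plans a SITES dataset, and institute type cannot enter a patient-level model without a link from patient to site. The downside is a wider interval and less apparent power for this one exploratory covariate. If retesting habits differ systematically by institute type, working at site level will not remove that confounding, and the report should say so.

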Univariate and multiple logistic regression (MLR) methods will be used to investigate the impact of various explanatory covariates (e.g. demographic and disease characteristics, co-morbidities, type of treating institution, and prior treatment for CHC and response outcome in treatment experienced patients) on SVR12. These analyses will be of exploratory nature, data driven, and will be performed for various CP analysis groups since not each covariate might be predictive in each patient group. Furthermore, the fact that treatment regimens will differ in the various patient groups has to be taken into account, when selecting the patient groups for each MLR analysis. Backward selection procedures will be applied to generate the final MLR models which will consider only covariates in the selection procedure with a p-value <0.25 in the corresponding univariate logistic regression analysis. A p-value <0.05 will be used for the covariates to stay in the model in a backward elimination step. Logistic regression methods will also be used to investigate the impact of treatment adherence on SVR12.

All safety variables will be summarized for patients in the SP using descriptive statistical methods stratified by the type of combination treatment and scheduled treatment duration.

Milestones:

Start of Data Collection:	October 2015
End of Data Collection for Interim Analysis:	December 2016
End of Data Collection for Final Report:	March 2017
Interim Analysis of Study Results:	March 2017
Final Report of Study Results:	June 2017

Confidential Information

No use or disclose outside AbbVie is permitted without prior written authorization from AbbVie

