The TURQUOISE-II [60] study explored the efficacy of the ABBVIE REGIMEN in the traditionally most difficult-to-treat cirrhotic patients. This large study enrolled exclusively genotype 1 infected patients with cirrhosis, including treatment-naïve and treatment-experienced individuals. All patients received the ABBVIE REGIMEN with RBV and were randomized to 12 or 24 weeks of therapy. Overall 92% and 96% of patients achieved SVR following treatment for 12 or 24 weeks, respectively. Analysis of subgroups demonstrated that the small difference in SVR between treatment arms was due largely to the subgroup of genotype 1a treatment-experienced prior null responders treated for 12 weeks who achieved an SVR of 80%. This subgroup of patients achieved an SVR of 93% when treated for 24 weeks. Among genotype 1a infected patients, partial responders and relapsers had higher SVR rates than null responders in the 12 week treatment group, while similar SVR rates were seen among the null responders, partial responders and relapsers treated for 24 weeks, suggesting that the longer duration of 24 weeks is required only for cirrhotic genotype 1a null responders. SVR rates were very high across all subgroups in genotype 1b treatment-experienced patients treated for 12 and 24 weeks.

Confidential Information

No use or disclose outside AbbVie is permitted without prior written authorization from AbbVie

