## 4.2.6.3 CHC treatment history

For treatment-experienced patients the most recent prior treatment and the outcome to prior treatment as reported by the investigator in the eCRF (Null response, Partial response, Breakthrough, Relapse, Sustained virological response (SVR) followed by reinfection, Discontinued [and none of the above], Unknown/ None of the above) will be summarized in frequency tables. In addition to the frequency of each medication (IFN alpha, PEG IFN-alpha, IFN NOS, PEG IFN NOS, Ribavirin, DAA), the frequency of the combinations (pegIFN alpha + RBV, pegIFN alpha + RBV + Telaprevir, XXX) will be summarized.

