  - o Depression (No [reference], Yes)

- Diabetes mellitus (No [reference], Type 1/Type 2)
- Hypertension (No [reference], Yes)
- Immunologically mediated disease (No [reference], Yes)
- Hypothyroidism (No [reference], Yes)
- Alcohol use (None [reference], Yes –occasional, Yes –regular, Exdrinker)
- Key clinical chemistry and hematology laboratory variables at baseline
  - o ALT ratio (continuous, see 4.2.6.5)
  - o AST ratio (continuous, see 4.2.6.5)
  - Platelets [10^9/L] (continuous)
- Prior treatment status (HCV treatment naïve [reference], HCV treatment experienced)

Additionally, an interaction term for cirrhosis status and genotype will be considered. If the most recent stage of liver fibrosis status (No cirrhosis/Transition to cirrhosis vs Cirrhosis), the genotype (G4, G1b vs G1a) or the interaction of both remains in the final model, then additional MLR might be considered for the subgroups concerned, taking into account the treatment regimen (e.g. in cirrhotic G1 patients: RBV vs no RBV and 12 wks vs 24 weeks).

The categories pre-specified above could be modified in the analyses if this is supported by the data (e.g. categories could be combined, if their impact on SVR24 is similar). Furthermore, continuous variables can be replaced by categorical variables.

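### The SAP's predictor model drops, without saying so, the protocol's covariates for prior hepatitis C treatment and its outcome, so it cannot separate prior null responders from other treatment-experienced patients

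*SAP*

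**What the plan says.** **Protocol.** Section 9.7.3.3 lists the covariates for the univariate and multiple logistic models. For treatment-experienced patients it names "Most recent prior treatment for CHC" and "Outcome of most recent prior CHC treatment". The abstract (section 4.0) repeats them as "prior treatment for CHC and response outcome in treatment experienced patients". Section 9.7.3.3 leaves further detail and additional covariates to the SAP. It does not mention removing any.

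**SAP.** The list under SVR24 (Exploratory Analyses) in 4.2.7.2.1 has one treatment-history entry: "Prior treatment status (HCV treatment naïve [reference], HCV treatment experienced"). Prior regimen and prior outcome are absent, and the text does not remark on it. Section 4.2.6.3 nevertheless summarises the "outcome to prior treatment as reported by the investigator in the eCRF", with null response, partial response, breakthrough and relapse as separate categories. That summary is a baseline table only.

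**Background.** Protocol 7.1 describes the phase III trial in cirrhotic genotype 1 patients. It says that the small SVR difference between 12 and 24 weeks came largely from the subgroup of "genotype 1a treatment-experienced prior null responders treated for 12 weeks who achieved an SVR of 80" per cent. The same subgroup reached 93% when treated for 24 weeks.

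**The concern.** Secondary objective 2 is to find predictors of virological response. The contrast in protocol 7.1 lies within the experienced group: among genotype 1a patients treated for 12 weeks, null responders did worse than partial responders and relapsers. A naive/experienced term averages over that contrast. Any effect of null response is carried in weakened form by the experienced category and may fail the p<0.05 criterion for staying in the model. A report that follows the SAP would then contain no test of prior response, although the protocol promised one and the data exist.

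The silence also matters. The SAP openly declares other departures from the protocol: the upper limit of the SVR12 window (4.1.1) and the replacement of the shift tables (4.2.8.4). A reader would take an undeclared deletion to mean that the protocol's list still stands.

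**Working it through.** **1. Is prior outcome related to response anywhere else in the SAP?** The protocol's core-population analysis groups included treatment-experienced versus naive (4.0, 9.7.2). The SAP's groups (4.2.1) use genotype and cirrhosis only, and response rates are stratified by those two (4.2.7.1, 4.2.7.2.1). No output title in SAP Table 8 gives response by treatment history. Table 7 covers treatment history at baseline, and Table 6 crosses prior-treatment status with regimen, not with response. On the listed titles, the binary regression term is the only pre-specified link between treatment history and SVR.

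**2. The plan's own figures.** The only study-size figures are the Clopper-Pearson widths in protocol Table 3 (SAP Table 1). Recomputed from beta quantiles for 340, 360 and 380 patients, they are 6.67, 6.47 and 6.29 points at 90% SVR12, and 4.95, 4.80 and 4.66 at 95%. The plan states 6.7, 6.5, 6.3 and 4.9, 4.8, 4.7, so they agree to within about 0.05 points. No figure is given for the predictor model. Expected failures are 360 × 0.05 = 18 to 380 × 0.05 = 19 at 95% SVR, and 360 × 0.10 = 36 to 380 × 0.10 = 38 at 90%.

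**3. Dilution.** Inputs: null-responder SVR of 80% or 93% (protocol 7.1); 95% in all others (assumption); share *s* of null responders among experienced patients (assumption, because the documents give none).

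- Failure in experienced patients: f_E = s × f_null + (1 − s) × 0.05
- Odds ratio for failure against naive: [f/(1 − f)] / [0.05/0.95]

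| Null-responder SVR | s | f_E | OR, experienced vs naive | OR, null response |
|---|---|---|---|---|
| 80% | 50% | 0.5 × 20 + 0.5 × 5 = 12.5% | 0.1429/0.0526 = 2.71 | 0.25/0.0526 = 4.75 |
| 80% | 30% | 0.3 × 20 + 0.7 × 5 = 9.5% | 0.1050/0.0526 = 1.99 | 4.75 |
| 93% | 50% | 0.5 × 7 + 0.5 × 5 = 6.0% | 0.0638/0.0526 = 1.21 | 0.0753/0.0526 = 1.43 |
| 93% | 30% | 0.3 × 7 + 0.7 × 5 = 5.6% | 0.0593/0.0526 = 1.13 | 1.43 |

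**4. What that does to power, at the 80% end.** Assume 370 patients, 30% or 50% experienced (111 or 185), and null responders making up 10% to 50% of those. Exact power of a two-sided Fisher test at 0.05:

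- experienced vs naive: 6% to 67%
- null responders vs all others: 39% to 97%, higher than the binary comparison in all eight scenarios
- null responders vs other experienced patients: 37% to 89%, higher in seven of eight. The exception is 111 experienced with 56 null responders, at 59% against 66%.

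These are single-factor tests. The SAP's multivariable model with backward selection would not match them exactly.

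**The case against.** **The 80% is narrow.** It belongs to cirrhotic genotype 1a null responders treated for 12 weeks. Protocol 7.1 reports similar rates across prior-response types at 24 weeks, very high rates in all genotype 1b experienced subgroups, and 96% in non-cirrhotic experienced genotype 1a patients given the regimen with ribavirin. Giving 80% to every null responder is the favourable end of the illustration. This stands, and is why the 93% rows are shown.

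**Other predictors are documented and modelled.** A reader might infer that null response is the only predictor in the background. It is not. Protocol Table 1 shows, without ribavirin, 90% for genotype 1a against 99% for 1b, and section 7.1 gives genotype 4 as 91% without ribavirin and 100% with it. Genotype, cirrhosis and their interaction are in the SAP model.

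**Post hoc analysis remains possible.** A reader might also infer that a null-response effect could never be found. The SAP calls these analyses data driven and lets categories be modified, so the effect can still be examined. But its example of modification is combining categories, and it does not name prior outcome. The effect is therefore not pre-specified, rather than out of reach. Nor do the documents show that the report would call prior response non-predictive: the listed term is treatment status, and a negative result would concern only that.

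**Regimen.** A reader might go further and say that the SAP ignores regimen, contrary to the protocol's statement that the fact that "treatment regimens will differ in the various patient groups has to be taken into account". The documents do not support that. The protocol's requirement concerns choosing patient groups for each model. The core-population exclusions in SAP 4.2.1 already tie regimen in part to genotype and cirrhosis. The SAP also says that if either factor or their interaction stays in the final model, "then additional MLR might be considered for the subgroups concerned", taking regimen into account. Those models are optional, but forced ribavirin and duration terms would be a debatable preference that overlaps with covariates already present.

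**Few events.** With 18 to 38 failures, every added parameter costs precision. The SAP model also uses SVR24 with remaining missing values counted as failures, which weakens any virological predictor under either coding. This limits what the fix can deliver. It does not justify a silent deletion.

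**Conclusion.** The point holds as an undeclared departure from the protocol. Two named covariates are missing from the SAP model, the data for prior outcome are collected, and no listed output relates it to response. The pre-specified model can compare naive with experienced patients but cannot show a difference by prior response within the experienced group.

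The size depends on the null-responder rate and on their share of experienced patients, which the documents do not give. With 95% SVR in all others and a share of 30% to 50%, a failure odds ratio of 4.75 shrinks to between 2.0 and 2.7 if null responders reach 80%. If they reach 93%, 1.4 shrinks to between 1.1 and 1.2, and there is little to find under either coding.

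This affects one exploratory analysis that serves secondary objective 2. The primary SVR12 estimate is untouched. It should be corrected, but it does not threaten the study.

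**What to change.** In SAP 4.2.7.2.1:

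1. Replace the binary term with three levels: naive (reference), experienced without null response, and prior null response. State where an unknown prior outcome goes (for example, the second level) and repeat the model with those patients reassigned or excluded.
2. Add an exploratory model restricted to treatment-experienced core-population patients, with prior treatment type and prior outcome as candidate covariates, as protocol 9.7.3.3 lists them. Give a rule in advance for pooling sparse categories. Say how unknown outcomes count towards the SAP's 80% data-availability rule, so that the covariate is not lost by default.
3. If neither is wanted, declare the deletion as the SAP does for its other departures, give the reason, and state in the report that prior response was not tested.

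The cost is SAP wording and some programming on data already collected. The three-level term adds one parameter to the pooled model; the experienced-only model adds a few more on a smaller set of failures. Its estimates will be imprecise and should be reported with confidence intervals and described as exploratory.
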